## Study Design

A Phase II, double-blind, 2 arm pilot randomised placebo controlled trial. 50 patients will be randomised 2:1 to Axitinib or placebo.

Main Inclusion criteria: Chemo-refractory third-line metastatic CRC with US-assessable liver or other abdominal metastases that can have a baseline DCEUS baseline measurement.

Arm A: Axitinib monotherapy started in all patients at 5mg bd, and increased fortnightly by a dose level (See Table 4) as tolerated to a maximum dose of 10mg bd.

Arm B: Placebo at 2:1 ratio to treatment

Follow up: *Optional* visit at 48-72 hours post first dose for measurement of temperature, oxygen saturations, blood pressure and CEHPI. Outpatient monitoring at 2 weeks and 4 weeks post first dose and at 4 week intervals thereafter which will include medical history and examination, measurement of temperature, oxygen saturations and blood pressure, urinalysis and blood tests including GI profile and VEGF-PK samples. RECIST restaging at 8 weeks and at 8 weekly intervals thereafter. CEHPI will be performed at baseline, optionally at 48-72 hours, 2 weeks and 8 weeks for assessment of differential blood supply. At 8 weeks, after tumour CT RECIST assessments, conventional responders (CR/PR/SD) continue monotherapy. In non-responders (PD), monotherapy can be continued if patient chooses to continue and if tolerated.

[figure not shown]

Figure 1: Protocol for responders and non-responders to Axitinib at 8 week RECIST evaluation.

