## 9. Statistical Analysis

### 9.1 Size of treatment effect

This novel project is a Pilot Phase II double-blinded, placebo controlled randomised (2:1 Axitinib : Placebo) for 50 patients. This sample size would not normally allow for conventional or adequate powering of a study based on OS, PFS or RR. This is a pilot study of assessing efficacy of axitinib monotherapy in colorectal cancer. The primary end-point is PFS by conventional RECIST. If a difference of more than 6 weeks improvement in PFS is observed, then a funding application to Pfizer and UK NCRN will be made for an adequately powered phase III study.

As a secondary and exploratory analysis, the major interest is whether we can better select (or predict) the population that benefits from Axitinib within the next generation of study design. If our secondary hypothesis is correct, then in those patients who receive Axitinib, a significant proportion will have ultrasound detectable changes in reduction in blood flow. i.e. a significant pharmacodynamic effect on the tumour vasculature measured via the US biomarker index (CEPHI). In our preliminary work (Gauthier et al, 2011), a 20% change in CEPHI was significant and also allowed for measurement error. Thus, this study will therefore examine the survival difference between CEPHI responders (those whose CEPHI falls by  $\geq 20\%$ ) versus non-responders. A clinically meaningful difference in survival in these groups would be a difference of at least 6 weeks. If this end-point is achieved, it would be a positive signal to design an adequately powered phase III powered for OS. This would allow enrichment for patients who potentially benefit, but also allow discontinuation in patients at 2 weeks who will not benefit, saving unnecessary treatment and toxicities. This approach of personalised medicine using biomarkers (in this case CEPHI) is the direction of almost all cancer studies.

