The conventional PFS and OS for this cohort of chemo-refractory patients is 6-8 weeks and 4-6 months respectively. This is the first study with Axitinib in this setting. Our aim with 50 patients is to generate data for a sample size calculation for a randomised phase III. In the only comparative Phase 2 study (A6181003) with a similar compound, is of Sunitinib in chemorefractory metastatic colorectal cancer, 84 patients were enrolled and 82 were actually treated with Sunitinib. 10% discontinued due to adverse events. The ITT analyses for PFS was less than 2 months but OS still showed an encouraging overall survival of 10.2 months. Of greater interest, 1 patient with prior Bevacizumab therapy had a partial response; 24 patients (29%) had a best response of stable disease, 13 patients had SD  $\geq 22$  weeks. (This demonstrates the reason for doing our analysis as a sub-population has benefited significantly from Axitinib's parent compound and with CEPHI – we hope to predict this group). In our study, we would thus expect around 15-18 of the treated patients to have prolonged progression-free survival of this order of magnitude, and the placebo treated patients will act as a contemporaneous control. If the 2 week CEPHI index is highly predictive of survival in this group, then selection on this basis for a phase III trial will enrich the potentially benefitting population even further.

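### Section 9.1 triggers phase III on an observed PFS gain above 6 weeks and feeds phase III sizing from the same 50 patients, with no safeguard against carrying forward an inflated effect

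*Combined protocol and SAP*

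**What the plan says.** All of this is in the combined protocol and SAP.

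- **Size.** The Study Design summary states "50 patients will be randomised 2:1 to Axitinib or placebo", about 33 v 17. Section 9.1 concedes: "This sample size would not normally allow for conventional or adequate powering of a study based on OS, PFS or RR".
- **Purpose.** Section 9.1: "Our aim with 50 patients is to generate data for a sample size calculation for a randomised phase III". It does not say whether that means the treatment effect, the control median, event rates or drop-out.
- **PFS trigger.** Section 9.1: "If a difference of more than 6 weeks improvement in PFS is observed, then a funding application to Pfizer and UK NCRN" is to follow, for a properly powered phase III. No test or confidence limit is attached.
- **Second route.** For CEHPI responders against non-responders, section 9.1 says "A clinically meaningful difference in survival in these groups would be a difference of at least 6 weeks", and if this is reached, "it would be a positive signal to design an adequately powered phase III powered for OS".
- **Control outcome.** Section 9.1: "The conventional PFS and OS for this cohort of chemo-refractory patients is 6-8 weeks and 4-6 months respectively".
- **Analysis.** Section 9.2 makes the primary analysis a Kaplan-Meier comparison of PFS in patients who complete at least two weeks of therapy. Hazard ratios with 95% CIs are specified only for the CEHPI comparisons.

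**The concern.** A threshold on a noisy estimate selects the estimates that erred upward. Here the same 50 patients decide whether a phase III is sought and supply data for its size. Nothing in 9.1 or 9.2 prevents the selected gain from becoming the planning effect: no shrinkage, no conservative limit and no fixed target difference. A phase III planned on an inflated effect has too few events. Since supplying the phase III sample size is this trial's own stated aim, the matter cannot be left wholly to the later protocol.

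**Working it through.** The plan gives no alpha, power, effect or event count behind N = 50, so there is no figure of its own to reproduce.

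**Inputs from the documents:** 50 patients at 2:1; control PFS 6-8 weeks; trigger above 6 weeks; CT every 8 weeks.

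**Assumptions:** 6-8 weeks is a median; PFS is exponential; the trigger is read on the difference in medians (section 2.2 words the endpoint as median PFS); all 50 have events; no drop-out; phase III is 1:1 with 90% power at two-sided 0.05. True gains of 3-12 weeks are examined.

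**1. Noise in the pilot.** The standard error of the log hazard ratio is 1/√(50 × 2/3 × 1/3) = 0.30. An observed HR of 0.50 therefore has a 95% CI of 0.50 ÷ 1.80 to 0.50 × 1.80, or 0.28 to 0.90, since exp(1.96 × 0.30) = 1.80. A true 6-week gain is HR 6/12 = 0.50 to 8/14 = 0.57. Power is Φ(|ln HR|/0.30 − 1.96) = 64% and 46%.

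**2. One case by hand.** Phase III events at 90% power are 4(1.96 + 1.28)²/(ln HR)² = 42.03/(ln HR)². Take a control median of 7 and a true gain of 4 weeks, so the true HR is 7/11 = 0.636.

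- Events needed: 42.03/0.2043 = 206.
- Mean gain among simulated pilots that pass: 8.37 weeks. Planning HR: 7/15.37 = 0.455. Events planned: 42.03/0.619 = 68.
- Actual power with 68 events: Φ(√(68/4) × 0.452 − 1.96) = Φ(−0.10) = 46%. Averaging over the simulated pilots that pass gives 49%.

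**3. Simulation.** 40,000 pilots per scenario, exact progression times, ranges over control medians of 6, 7 and 8 weeks:

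| True gain (weeks) | Pilots passing | Mean observed gain if passing (weeks) | Phase III power, sized on the gain | Phase III power, sized on the rate ratio |
|---|---|---|---|---|
| 3 | 16-21% | 7.7-8.3 | 33-37% | 47-50% |
| 4 | 26-30% | 8.0-8.7 | 46-51% | 57-61% |
| 6 | 49-50% | 9.0-9.6 | 66-71% | 69-73% |
| 8 | 66-68% | 10.2-10.7 | 77-80% | 76-79% |
| 12 | 86-90% | 13.1-13.6 | 85-86% | 83-85% |

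Sizing on the gain means adding it to the 6-8 week control median.

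**4. Scan grid.** With progression recorded at 8-weekly scans, a true 4-week gain appears as 8.2-8.9 weeks. Power is 45-49% sized on the gain and 66-73% on the hazard ratio. At 6 weeks the figures are 9.0-10.0 weeks, 66-71% and 73-79%. With no true effect, the chance of passing rises from 1-3% to 9-25%.

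**5. Overall range.** Adding a third method, the observed ratio of the two medians, gives about 36-73% at a true gain of 4 weeks, 57-86% at 6 and 79-92% at 12. That method sets the lower ends with exact times. On the scan grid it sets the upper ends at 6 and 12 weeks, because rounding up the control median pulls the ratio towards 1.

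**6. Benchmark.** If every positive pilot estimate were carried forward with no 6-week gate (exact times, sized on the gain), power would be 81-84% at a true gain of 6 weeks and 87-88% at 12. Selection accounts for the rest of the drop in the table.

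**The case against.** The strongest reply is that the harmful step is not in the text. Section 9.1 speaks of data for a sample size calculation. Control-arm PFS, event rates and drop-out would fit that description, and the phase III would have its own protocol and justification. This stands: a reader might infer that the phase III would be underpowered, but the documents support only a conditional statement.

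A reader might also infer that the PFS gate is the sole way forward. Section 9.1 does not say so. It has a second route through CEHPI responders to a phase III powered for OS, which would not simply inherit the PFS ratio and is not modelled here. That route also rests on an observed difference.

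Third, the size depends on the truth. Taking true hazard ratios of 0.7-0.8 gives phase III power as low as 18-40% when sized on the medians. With a control median of 6-8 weeks, those are true gains of only 6/0.8 − 6 = 1.5 to 8/0.7 − 8 = 3.4 weeks, well below the plan's own threshold. They should not stand as the headline.

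Finally, section 9.1 openly disclaims conventional powering, and no analysis or participant in the pilot is affected. Both are true, but neither settles how the estimate is to be used afterwards.

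**Conclusion.** The concern holds as a conditional one. The observed PFS gain, given that it passed the 6-week gate, exceeded the true gain in every scenario examined. If it is carried forward unadjusted, the shortfall from 90% power is large at true gains of 3-4 weeks, moderate at 6 and small at 12. On the scan grid at 12 weeks, sizing on the median ratio can even slightly exceed 90%. Part of each shortfall is ordinary estimation noise. These sizes rest on the assumptions listed, chiefly exponential PFS and full event ascertainment.

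One further inference fails. From (8 + 6)/8 = 1.75 and (6 + 6)/6 = 2.0, a reader might conclude that every passing pilot must show a median ratio of at least 1.75-2.0. That treats the control median as fixed. With about 17 controls it varies, and simulated pilots pass with ratios down to 1.33-1.5.

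The gap in the plan is that 9.1 does not say which pilot quantities feed the phase III, and 9.2 provides no interval for the comparison that triggers it.

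**What to change.** In sections 9.1 and 9.2:

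1. Report the axitinib v placebo PFS hazard ratio with its 95% CI in all randomised patients, alongside the 6-week criterion. The set restricted to at least two weeks of therapy can be kept as a separate analysis.
2. State that the phase III will not be sized on the unadjusted pilot point estimate or the observed medians. Size it on a pre-set minimum worthwhile difference, or on a conservative confidence limit or shrunken estimate. The choice among these is the sponsor's.
3. State that the pilot directly supplies control-arm PFS, drop-out and scan completion.

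For scale, a pre-set 6-week gain over a control median of 6-8 weeks needs 88-135 events for 90% power. It removes the upward selection, but power is 65-67% if the true gain is 4 weeks and 45-48% if it is 3. The pre-set difference should therefore be the smallest gain worth detecting.

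The cost is a few sentences and one added estimate, with no change to trial conduct. The downside is a possibly larger, less favourable phase III sample size.

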## 9.2 Statistical analysis plan

The primary analysis will be on PFS by Kaplan-Meier of patients who manage to complete at least 2 weeks of Axitinib therapy (versus Placebo).

For the secondary analyses:-

A stratified log-rank test (1-sided,  $p=0.025$ ) will be used to compare PFS between CEHPI responders and non-responders. The median event time and 2-sided 95% CI for the median will be provided. The hazard ratio and its 95% CI will be also estimated.

The optimum CEHPI cut-point for determining response will be confirmed using the percentage change in CEHPI against RECIST response using a receiver operator characteristic curve. Test statistics including sensitivity, specificity, positive predictive value, negative predictive value, odds of disease progression and area under the curve will be calculated for 2 week CEHPI reduction in predicting disease progression.

A similar analysis will be performed with diastolic blood pressure.

Overall survival is defined as the time from date of randomisation to date of death due to any cause. For patients not expiring, their survival times will be censored at the last date they are known to be alive. Patients lacking data beyond the day of randomisation will have their survival times censored at the date of randomisation with duration of 1 day. Overall survival will be summarised using Kaplan-Meier methods and displayed graphically where appropriate. A stratified log-rank test (1-sided,  $p=0.025$ ) will be used to compare OS between CEHPI responders and non-responders. The median event time and 2-sided 95% CI for the median will be provided. The hazard ratio and its 95% CI will be also estimated.

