#### **Secondary objectives of trial**

- To assess the correlation in patients with a confirmed vascular response (as evaluated by a greater than 20% reduction in CEPHI at 2 weeks).
  - This assessment will be done by separating out the RECIST-progressors (non-responders) who can also be detected by CEPHI at 2 weeks, and comparing this with RECIST responders (CR+PR+SD). The patients receiving Placebo will be included in this analysis.
  - To demonstrate the value of CEPHI as an early imaging selection biomarker of non-response (or response) in patients who have had at least 4 weeks of study treatment.
- To compare overall survival between the treatment and placebo arms
- To compare the overall RECIST response rate between the treatment and placebo arms
- To compare and correlate the 2 week CEPHI and 8 week RECIST response rates.
- To compare the median overall survival of patients receiving Axitinib who develop new diastolic hypertension (>90mmHg) with those that do not (in either/or the blinded placebo group or treatment group combined)
- To identify if CEPHI will function as a non-invasive correlative biomarker of Axitinib pharmacokinetics (PK) and help minimise toxicity and identify responders

CONFIDENTIAL

- Toxicity (CTC) i for the treatment and placebo arms

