## 2.2 ENDPOINTS

### Co-Primary Endpoints

- To assess whether the median progression-free survival is longer in third-line patients with chemo-refractory metastatic colorectal cancer receiving Axitinib monotherapy Versus placebo
- To assess whether the median progression-free survival is shorter in those patients who do not undergo vascular shutdown (defined as  $\leq 20\%$  reduction in CEHPI at 2 weeks) compared with those that do undergo vascular shutdown ( $>20\%$  reduction in CEHPI at 2 weeks).

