### Secondary Endpoints

- To compare overall survival between the treatment and placebo arms
- To compare duration on study treatment between the treatment and placebo arms
- To compare the best overall RECIST response rate between the treatment and placebo arms
- To compare and correlate the 2-week CEHPI perfusion index and 8 week RECIST response rates in the ITT population
- To compare the median overall survival of patients receiving Axitinib who develop new diastolic hypertension ( $>90\text{mmHg}$ ) with those that do not (in either/or the blinded placebo group or treatment group combined)
- To identify if CEHPI will function as a correlative biomarker of Axitinib pharmacokinetics (PK) and help minimise toxicity and identify responders
- To compare toxicity (CTC) information for the treatment and placebo arms.
  - Type, incidence, severity, timing, seriousness of adverse events by Chemotherapy toxicity criteria (CTC) v4.03 grading.
- Axitinib PK analysis correlation with patients developing or not developing diastolic hypertension

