### 3. Study Design

A Phase II, double-blind, 2 arm pilot randomised placebo controlled trial. 50 patients will be sequentially randomised 2:1 to Axitinib or placebo.

Inclusion criteria: Chemorefractory third-line metastatic CRC with US-assessable liver or other abdominal metastases that can have a baseline DCEUS baseline measurement.

Treatment arm: Axitinib monotherapy started in all patients at 5mg bd, and increased fortnightly by a dose level (See Table 4) as tolerated to a maximum dose of 10mg bd.

Control arm: Placebo (blinded) randomised 2:1 to Axitinib : placebo

Follow up: Outpatient monitoring at 2 weeks and 4 weeks post first dose then 4 weekly thereafter with RECIST restaging every 8 weeks. CEHPI at baseline, 2 weeks and 8 weeks for assessment of differential blood supply (CEHPI) with an optional visit at 48-72 hours post first dose. VEGF-PK samples at Day 15 & Day 28 and at 8 weeks and RECIST progression. At 8 weeks, after tumour CT RECIST assessments, conventional responders (CR/PR/SD) continue monotherapy. In non-responders (PD), monotherapy can be continued if patient chooses to continue and if tolerated. CT response assessments continue at 8 weekly intervals in all patients, with parallel 8 weekly DCE-US. CEHPI at baseline, optionally at 47-72 hours, 2 weeks, 8 weeks and at progression of disease.

[figure not shown]

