### **6.3 End of Treatment**

The study treatment may be permanently discontinued upon progression of disease, occurrence of unacceptable toxicity, withdrawal of consent, or another withdrawal criterion, unless there is sufficient evidence of clinical benefit to justify continuation of study treatment at the discretion of the investigator. However, patients who require different cancer treatment from that assigned at randomisation must be withdrawn from the study and followed as described below.

After discontinuation of study treatment and the mandated 28-day follow-up period, patients will be followed in order to collect information on further anti-tumour therapy and survival. Patients discontinuing study treatment without documented evidence of disease progression should continue tumour imaging assessments at the same frequency until disease progression, or initiation of another anticancer treatment, whichever is earlier.

The primary reason for a patient's discontinuation of the test drug will be clearly documented on the CRF. Assessments should be performed as outlined in the patient schedule above. At the end of the study or at withdrawal, the following procedures should be performed if they were not performed during the last week:

- Physical examination of major body systems, ECOG performance status, body weight, and vital signs
- Haematology, blood chemistry, coagulation tests, and urinalysis
- CT or MRI scans of chest and abdomen in addition to any other applicable sites of disease
- Assessment of adverse events. Adverse events that are serious, suspected to be related to study drug, or considered significant by the investigator must be followed after the time of therapy discontinuation until the event or its sequelae resolve or stabilise at a level acceptable to the investigator or his/her designated representative. Each serious adverse event (SAE) must be reported to the Imperial College, Pfizer, MHRA and REC
- Assessment of concomitant medications and treatments
- Assessment of Axitinib/placebo compliance/accountability

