## **7. Assessments**

### **7.1. Efficacy Assessment**

Baseline (screening) tumour assessments require CT/MRI (no chest x-ray) of the chest and abdomen at the minimum. If the interval between any of the baseline tumour assessments and randomisation were to become >28 days, the expired baseline tumour imaging must be repeated. At baseline, tumour lesions will be categorized as target or non-target. All patients will be evaluated for response according to RECIST version 1.1.

CT or MRI of brain at screening and subsequent imaging of brain may be performed if clinically indicated as determined by the treating physician. Bone scan at screening and subsequent imaging of bone may be performed if clinically indicated as determined by the treating physician.

For all patients, CT/MRI (covering the same anatomy as the baseline scans, except brain) will be required every 8 weeks by calendar.

Response (CR/PR) requires confirmation with CT/MRI at least 4 weeks after the response is first noted. These tumour assessments must be performed as scheduled until progression of disease or death regardless of whether patient is receiving study medication or not until permanent withdrawal from study treatment. If a patient is to start a new therapy, these tumour assessments should be repeated prior to start of the new therapy.

The same method and technique should be used to characterize each identified and reported lesion at baseline and during the study treatment period. Imaging-based evaluation over clinical examination is the required technique when both could be used to assess the anti-tumour effect of the treatment. Clinical evaluation of superficial lesions should not be used for tumour measurement. Tumour evaluation by positron emission tomography (PET) scan or by ultrasound may not substitute for CT or MRI scans.

If a patient develops new or worsening pleural effusion or ascites that is large enough for thoracentesis or paracentesis, a fluid sample should be obtained for cytological examination to determine whether the fluid collection is malignant unless there is a reasonable clinical contra-indication to do so. If fluid cytology is negative for malignant cells (defined as non-positive for presence of malignant cells, including “negative”, “atypical” or “indeterminate”), then the new or enlarging fluid collection alone should not be used as evidence of PD. If fluid cytology is positive (including “positive” or “malignant”), then “PD” will be assigned.

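### The primary PFS analysis selects patients on completing 2 weeks of treatment, an event after randomisation, and no all-randomised PFS analysis is planned

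*Combined protocol and SAP*

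**What the plan says.** The trial randomises 50 patients: "50 patients will be sequentially randomised 2:1 to Axitinib or placebo" (section 3). Section 9.1 names the endpoint: "The primary end-point is PFS by conventional RECIST". Section 2.2 frames the first co-primary comparison without any condition on time treated: "To assess whether the median progression-free survival is longer in third-line patients with chemo-refractory metastatic colorectal cancer receiving Axitinib monotherapy Versus placebo".

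Section 9.2 then restricts the analysis: "The primary analysis will be on PFS by Kaplan-Meier of patients who manage to complete at least 2 weeks of Axitinib therapy (versus Placebo". It does not say whether the condition also applies to placebo, what counts as completing 2 weeks when dosing is interrupted, or whether PFS runs from randomisation or from week 2. A time origin and a censoring rule are given for overall survival only.

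Elsewhere the populations differ again. A secondary objective on the ultrasound index (CEHPI) is set "in patients who have had at least 4 weeks of study treatment", while a related secondary endpoint reads "To compare and correlate the 2-week CEHPI perfusion index and 8 week RECIST response rates in the ITT population". That endpoint is the only one of this trial's own analyses for which an ITT population is named.

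On imaging after treatment stops, 7.1 says assessments go on "regardless of whether patient is receiving study medication or not until permanent withdrawal from study treatment". Section 6.3 says patients who stop without progression "should continue tumour imaging assessments at the same frequency until disease progression", or until another anticancer treatment starts.

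**The concern.** Completing 2 weeks of drug is known only after randomisation. It depends on survival, tolerance and early deterioration, all of which treatment can affect. Removing the patients who fail this condition breaks the balance that randomisation provides. If they are removed from the Axitinib arm only, that arm loses its earliest deaths while placebo keeps its own, and PFS looks longer on Axitinib without any drug effect.

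The trial is an unpowered pilot, so the harm is mainly to an estimate. That estimate has consequences, however. Section 9.1 ties a phase III funding application to an observed PFS gain of more than 6 weeks, and also says the data are to feed the phase III sample size. Section 6.4 says patients who leave early are not replaced, so each exclusion also shrinks a small trial.

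**Working it through.** The plan gives no power, event count or test for the Axitinib-placebo comparison, so there is no stated figure to reproduce. The check sizes the filter.

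**Inputs.**
- Arms: 50 × 2/3 ≈ 33 Axitinib and 50 × 1/3 ≈ 17 placebo (section 3).
- Control medians: PFS 6-8 weeks, OS 4-6 months (9.1). In weeks, OS is 4 × 52/12 = 17.3 to 6 × 52/12 = 26.
- Scans: first scheduled CT at week 8, then every 8 weeks (Schedule of Activities; 7.1).
- Decision rule: observed PFS gain above 6 weeks (9.1).
- Assumed: exponential times, and a one-sided 0.025 log-rank. Section 9.2 states that level only for CEHPI responders against non-responders.

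**Step 1: who is dropped.** The share with an event before week 2 is 1 − 0.5^(2/median).
- Deaths: 1 − 0.5^(2/17.3) = 0.077 and 1 − 0.5^(2/26) = 0.052. Times 33, this is 2.5 and 1.7 Axitinib patients.
- All progressions and deaths, if progression were seen as it happens: 0.206, 0.180 and 0.159 for medians of 6, 7 and 8 weeks. Times 33, this is 6.8, 5.9 and 5.3.

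The second count does not fit this trial, because few RECIST progressions can be recorded before a first CT at week 8. Those dropped would mainly be early deaths, clinical deteriorations, toxicity drop-outs and withdrawals.

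**Step 2: effect under no true difference.** Simulation of 33 against 17 patients. In the 8-weekly rows, the death hazard follows the OS median, progression makes up the rest of the PFS hazard and is recorded at the next scan, and deaths count on their exact date. In the continuous rows, every event is seen when it occurs.

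| Case | Axitinib dropped | Average difference in medians, Axitinib minus placebo | One-sided 0.025 rejection | Chance of gain above 6 weeks |
|---|---|---|---|---|
| 8-weekly scans, all randomised | 0 | reference | about 3% | about 1-11% |
| 8-weekly scans, deaths before week 2 removed, Axitinib only | 1.7-2.5 | shifts by about 0.3-1 week | about 5-7% | about 3-16% |
| Continuous, all randomised | 0 | −0.1 to −0.2 week | 3.2-3.4% | 0.6-3.1% |
| Continuous, all events before week 2 removed, Axitinib only | 5.3-6.8 | about 1.9 weeks | 10.7-13.9% | 6.1-12.0% |
| Continuous, same filter in both arms | 5.3-6.8 | about −0.2 week | about 3.5% | 1.3-4.1% |

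Ranges run over PFS medians of 6, 7 and 8 weeks and, in the 8-weekly rows, OS medians of 4 and 6 months.

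The continuous Axitinib-only case can be checked by hand: for an exponential time, the median given survival past week 2 is the original median plus 2 weeks. The 6-week rule is passed by chance more often on the 8-weekly grid, even with everyone included, because medians tend to jump between scan dates.

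**The case against.** The strongest reply is that the effect is small and perhaps absent. Much of this stands.

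- **Scan timing.** A reader might infer a 2-week gain and a false-positive rate of about 12%. Those figures need continuously observed progression, and the first CT is at week 8. Even with deaths removed, the shift in a typical simulated run is only 0-0.2 week, because medians cluster at the week-8 scan; the 0.3-1 week is an average over runs. Entry limits such as ECOG 0-1 may make early deaths rarer than an exponential curve implies.
- **Toxicity drop-outs.** They are not PFS failures, so removing them does not by itself lengthen PFS.
- **Both arms.** The protocol sometimes writes Axitinib where it means blinded study drug (5.8), so the filter may be meant for both arms. With equal early loss the average bias is then near zero. Toxicity of the active drug could still make the loss unequal, and the wording leaves the choice open.
- **Formal error rate.** No test or level is stated for this comparison, so the rejection rates only illustrate.

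Three further inferences are not supported. First, 7.1 might suggest that scans of toxicity drop-outs are lost. Sections 5.10, 5.11, 5.12, 6.3 and 6.5.1 continue tumour assessment after treatment stops, so 7.1 is a clash of wording, not a likely loss of data. Second, the 4-week condition might seem to remove the early progressors. It sits in a secondary objective, and most patients found to have progressed at week 8 can have had 4 weeks of treatment. Third, section 1.2 might suggest stratifying by prior bevacizumab. All treated patients in that study received sunitinib, so it cannot separate prognosis from a difference in drug effect.

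None of this supplies an all-randomised PFS analysis.

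**Conclusion.** The sentence in 9.2 should be replaced. It makes the primary comparison conditional on an event after randomisation, departs from the co-primary endpoint in 2.2, and leaves no all-randomised PFS analysis to fall back on.

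The likely size is modest: about 2-3 of 33 Axitinib patients dropped and an average shift of about 0.3-1 week against a 6-week threshold, with a higher chance of a false pass. This rests on the Axitinib-only reading, exponential times, the plan's own medians and removal of deaths only. The documents give no rate of early discontinuation for this trial, so these are illustrative ranges. The shift of about 2 weeks and the 11-14% rejection are an upper bound that needs progression to be observed continuously. A filter applied equally to both arms would leave little average bias, but the comparison would still not be as randomised.

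**What to change.** Replace the first sentence of 9.2 with: *The primary analysis is PFS from randomisation to RECIST progression or death in all randomised patients, by allocated arm, using Kaplan-Meier with hazard ratio and 95% CI; patients without an event are censored at their last tumour assessment.* State also how a patient with no scan after randomisation is handled; 9.2 already has such a rule for overall survival.

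Keep the 2-week-completer analysis as a sensitivity analysis, with the same rule in both arms and time measured from week 2.

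Reconcile the clause in 7.1 on permanent withdrawal from treatment with 5.10-5.12, 6.3 and 6.5.1.

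The cost is wording in 9.2 and 7.1, agreed before unblinding. It needs no extra patients, and the imaging is already required by the other sections. The downside is that the estimate may be slightly less favourable to Axitinib.
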